Modeling. A longitudinal model fitted with linear mixed methods will be used for each outcome. Numerical outcomes with markedly non-normal distributions, if any, will be modeled with more appropriate error distributions than the default normal (e.g., lognormal or generalized beta distributions). The focus of inference will be the between-group difference in outcome trajectories over the study time points, modeled by a time by group interaction. A random effect for subject will be fitted to account for covariance among repeated measures on the same individuals. If necessary, we will conduct covariate adjustment for baseline factors unbalanced between the groups or predictive of dropout. Time will be modeled as a categorical variable, to avoid the strong assumption of linear trajectories, and therefore the single test for the interaction effect will be a multiple-degree of freedom test. Model-predicted outcome means (a.k.a. LS-Means) by group at each time point will be computed to facilitate interpretation. The overall treatment effect will be computed as the between-group difference in change from baseline (change from T1 averaged over T2 to T4) estimated with a linear contrast.

Handling of Missing Data

Mixed modeling techniques and covariate adjustment will reduce the impact of missing data, as the missingness is not assumed completely at random (MCAR) but conditionally (on the covariates) at random (i.e., MAR, a milder assumption).[82] Should dropout exceed the 20% allowed by the sample size (section C.7.5), non-parametric multiple imputation[83] will be employed to determine the robustness of the conclusions for the main analyses under the milder MAR assumption. Because missing data due to non-ignorable or non-random drop out (i.e., MNAR) does not depend on the observed data, it presents the most complex situation to handle. Because of the non-invasive, supportive nature of the BA/PS intervention, as well as the attention control condition, *a priori*, we do not expect to encounter non-random dropout (and therefore MNAR). However, we will examine the tracking system records and logs with regard to dropout, to determine the main reasons for dropout. If sufficient indication of an MNAR mechanism is found, sensitivity analyses under different assumptions for the missing data mechanism will be conducted, following the methodology described by Molenberghs and Kenward[84] in which the missing data mechanism needs to be modeled explicitly.

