Recursive partitioning. The classical approach to moderator or subgroup analysis consists of 3 steps: 1) pre-specifying some population characteristics of interest (e.g., site: UAB vs. D-H; race: minority vs. white; age: <65 vs. ≥65; source of participation restriction: primarily related to or unrelated to cancer; relapse vs. not, etc.); 2) analyzing one characteristic at a time, conducting inferences on differential intervention effects based on the characteristic's subgroups, using interaction tests adjusted for subgroup imbalances in other characteristics; and 3) applying an adjustment for multiple inference to account for the multiple analyses on the same body of data. Instead of implementing the classical approach, we propose using recursive partitioning, a.k.a. CART[86] (Classification and Regression Trees), a non-parametric modeling approach that allows extracting multivariate profiles from a sufficiently large dataset under minimal modeling assumptions, based on values of an outcome and participant characteristics. We propose this approach instead of the classical approach because multiple patient characteristics might be simultaneously associated with benefitting from the BA/PS intervention, therefore the multivariate approach can potentially provide more information and be more useful than the classical approach. Because CART is data-driven, these analyses will be considered exploratory. To avoid assuming that missing outcome data due to dropout is missing completely at random (i.e., MCAR), a Random Forest-based algorithm[83, 86] will be used to generate 3 imputed datasets comprising

baseline characteristics, group assignment, and longitudinal outcome variables. CART modeling will be implemented on each imputed dataset and results will be compared as a form of sensitivity analysis. The target variables for the CART modeling will be the average change from baseline in each primary outcome. Regression tree models for these target variables will be fitted using as predictors the group assignment and selected baseline characteristics. These baseline characteristics will include indicators of pertinent subpopulations of interest: site, race, income, age, etc. We will implement the conditional inference approach[87] to fit the tree models and use repeated 10-fold cross-validation to determine the final tree size. The tree model is a decision-tree-like structure that is interpreted based on the characteristics of the resulting groups of participants.

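### Random-forest imputation with group as an ordinary variable would shrink the treatment and moderator effects in the exploratory tree data sets, and in the robustness check if a forest is used there

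*Combined protocol and SAP*

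**What the plan says.** All the relevant text is in Section 9 of the combined protocol and SAP.

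- **Heterogeneity of Intervention Effects (Recursive partitioning).** To avoid assuming that dropout is completely at random, "a Random Forest-based algorithm[83, 86] will be used to generate 3 imputed datasets comprising" "baseline characteristics, group assignment, and longitudinal outcome variables". A tree is fitted to each imputed set and the results are compared as a form of sensitivity analysis. On the target: "The target variables for the CART modeling will be the average change from baseline in each primary outcome". Group and selected baseline characteristics are the predictors. On status: "Because CART is data-driven, these analyses will be considered exploratory".
- **Handling of Missing Data.** "Should dropout exceed the 20% allowed by the sample size", "non-parametric multiple imputation[83] will be employed to determine the robustness of the conclusions for the main analyses". No forest is named and no imputation variables are listed.
- **Modeling.** "A longitudinal model fitted with linear mixed methods will be used for each outcome". The overall effect is the between-group difference in change from baseline ("change from T1 averaged over T2 to T4) estimated with a linear contrast"). No imputation is involved.

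Neither imputation paragraph says whether the arms are imputed together or separately, and no forest settings are given.

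**The concern.** Group is listed beside baseline characteristics and repeated outcome scores. If both arms go into one forest, group is just one candidate split. The assumed effect is 3.94/10 = 0.39 SD, whereas the repeated scores are numerical and, at the higher planned correlations, much stronger predictors. Many trees will therefore leave group unsplit, at least along the branch where a given missing score falls. The donor for a missing BA/PS score can then be a control participant, and the reverse.

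This does not need informative dropout. It comes from an imputation model that smooths over the treatment contrast which the later analysis is meant to estimate.

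The trees exist to find group-by-covariate structure, which such a forest represents even less well than the main effect. The planned comparison across three imputed sets shows only random variation between imputations, not a bias common to all of them. If the same algorithm serves the robustness check, a smaller imputed effect could be misread as fragility of the mixed-model result.

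**Working it through.** **Inputs from the plan (Section 9, Sample Size Determination).** Minimally important differences 3.94 (satisfaction), 3.95 (ability) and 11.2 (quality of life); SD 10 for PROMIS and 24 for FACT-B; planning level .05/3 = .017; 80% power; three post-baseline visits; within-subject correlation 0.2 to 0.8; 300 women randomised 1:1; about 20% attrition.

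**The plan's own figures.** For a time-averaged difference with two-sided alpha (sidedness is assumed), n per arm = 2·SD²·(z₁₋α/₂ + z₀.₈₀)²/δ² × (1 + 2ρ)/3.
- PROMIS: 62.7 → 63 at ρ = 0.2 and 116.4 → 117 at ρ = 0.8.
- FACT-B: 44.7 → 45 and 83.0 → 83.

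All four agree with the plan. It gives no figure for imputation bias, so that was simulated.

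**Assumptions not in the plan.** Chained forests of 10 trees, with donors drawn from the leaves; 2 to 15 baseline variables; a constant effect of 3.94 at T2 to T4; 150 women per arm; monotone dropout. The estimate is the change-from-T1 contrast averaged over T2 to T4.

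**Simulation A: completely random dropout, 100 to 120 runs per setting.**
- 25% dropout (about 17% of post-baseline scores missing): pooled bias −0.30 to −0.43 over ρ 0.2 to 0.8, 5 or 12 baseline variables, and one third or all predictors tried per split.
- 35% dropout, ρ = 0.5: full data 3.99, pooled 3.41, by arm 4.00, so the pooled bias is −0.58.
- By-arm bias across settings: −0.07 to +0.07 (Monte Carlo SE 0.03 to 0.05).

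**Simulation B: separate code, dropout dependent on baseline score, 32 to 40 runs per setting.** Differences are from the same data before deletion (Monte Carlo SE 0.04 to 0.08).

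| Missing at T2/T3/T4 | ρ | Covariates | Full-data effect | Pooled | Group left out | By arm |
|---|---|---|---|---|---|---|
| 8/15/20% | 0.5 | 8 | 3.79 | −0.31 | −0.40 | −0.01 |
| 8/15/25% | 0.5 | 8 | 3.67 | −0.34 | −0.50 | +0.08 |
| 15/22/30% | 0.5 | 8 | 3.87 | −0.49 | −0.76 | +0.01 |
| 25/25/25% | 0.5 | 8 | 4.12 | −0.67 | −0.95 | 0.00 |
| 8/15/25% | 0.2 | 8 | 4.00 | −0.38 | −0.64 | −0.07 |
| 8/15/25% | 0.8 | 8 | 3.95 | −0.50 | −0.60 | −0.12 |
| 8/15/25% | 0.5 | 2 | 4.09 | −0.19 | −0.44 | +0.11 |
| 8/15/25% | 0.5 | 15 | 3.84 | −0.40 | −0.51 | −0.04 |

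The pooled loss runs from 0.19/4.09 = 5% to 0.67/4.12 = 16%.

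**Plausibility.** If imputed values carried none of the effect, the loss would be the missing fraction times the effect. With 25% missing at every visit that is 0.25 × 4.12 = 1.03, and leaving group out gave 0.95. Including group as a column cut this only to 0.67. The mechanism and its size fit together.

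**Moderator effect.** A true interaction of 7.88 (effect 0 in one half of the sample, 7.88 in the other), ρ = 0.5, completely random dropout, 30 runs per setting:
- 8/15/20%: pooled −0.85, by arm −0.52.
- 8/15/25%: pooled −1.16, by arm −0.88.
- 25/25/25%: pooled −1.87, by arm −1.23.

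The pooled loss is 0.85/7.88 = 11% to 1.87/7.88 = 24%. The by-arm loss is 7% to 16%. Imputing by arm therefore removes 39%, 24% and 34% of the loss, or about a third.

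**The case against.** The strongest reply is that the plan is under-specified rather than wrong. The list describes what the imputed data sets contain, and imputing by arm and recombining would also yield data sets containing group. This is fair as a matter of wording. But the pooled run is the natural execution of that sentence, and it biases in one direction, so silence is not harmless here.

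The second reply concerns the robustness check. A reader might infer that it too is a forest, since both paragraphs cite reference 83. The documents do not establish this. Reference 83 is a general chained-equations paper. The reference whose title names random forests is 86, which only the moderator paragraph cites. The check also runs only if dropout exceeds the roughly 20% expected. This objection stands, so that half of the point is conditional.

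Third, a reader might infer that the bias could overturn significance, for example by taking 0.4 from an estimate of 2.5 with SE 1, moving p from .012 to .036 across .017. This does not hold:
- The .017 level is for sample size. The analysis uses a 10% false discovery rate; with three primary tests (assumed), the Benjamini–Hochberg cut-offs are .033, .067 and .10.
- The loss shrinks with the effect. At a true effect of 2.5 (ρ = 0.5, 25% dropout, 50 runs) it was 0.26 (SE 0.05), giving z = 2.24 and p = .025, below the strictest cut-off.
- At the planned effect, the complete-data SE with 150 per arm is √{(2/150)·100·[(1 + 2ρ)/3 + 1 − 2ρ]} = 1.19, 0.94 and 0.60 for ρ = 0.2, 0.5 and 0.8. Then (3.94 − 0.43)/SE = 2.9, 3.7 and 5.9. A loss of 0.58 with the largest SE inflated by 15% still gives z = 2.45, p = .014.

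It would also be too strong to say that imputed values carry little of the effect. From Simulation A, they carry 1 − (0.43/3.94)/0.17 = 36% to 1 − (0.30/3.94)/0.17 = 55%.

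**Conclusion.** The point holds for the moderator data sets, on the natural reading that both arms are imputed together. The treatment effect in those sets shrinks by about 0.2 to 0.7 of 3.94 points at 20% to 35% dropout, and group-by-covariate effects are diluted further. The direction was the same in every setting tried. The size depends on forest settings, covariate count and dropout timing, none of which the plan gives; with two covariates it was only 0.19.

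For the robustness check the point is conditional on a forest being used. If so, the check would be modestly biased toward no effect and could understate robustness.

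A reader might go on to infer that the primary result is at risk. It is not: the primary analysis is a mixed model on all available data without imputation. The trees are declared exploratory, and no reversal of a significance decision has been shown. This is a worthwhile correction to secondary and exploratory analyses, not a threat to the trial's main conclusion.

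**What to change.** In the recursive-partitioning paragraph, state that imputation is run separately within each randomised arm and that the arms are recombined before any tree is fitted. In Handling of Missing Data, name the algorithm; if it is a forest, apply the same rule before fitting the mixed model. State the forest settings in both places.

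By-arm imputation removes the main-effect bias but only about a third of the moderator dilution. The tree results should therefore be reported with the limitation that true moderator effects may be understated.

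The cost is a small change in code and slightly noisier imputation, since each forest is built on about 150 women. In a further check, root mean squared error was essentially unchanged. No new data or design change is needed.

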Participation ability (secondary outcome): We will use the second 8-item PROMIS scale entitled *Ability to Participate in Social Roles and Activities Short Form 8a*[36, 37] to measure the ability aspect of participation. The scale was developed in conjunction with the satisfaction scale, as described above. We added an item to solicit participant perceptions of the degree to which their challenges are related to cancer or its treatment so that we can determine if the source of the restrictions moderates the effect of the intervention.

Productivity (secondary outcome): We will use relevant questions from the Disability Days section of the *Medical Expenditure Panel Survey (MEPS)* [38, 56] to capture days missed from work and lost household productivity. Missed days of work have been defined as half or more of a day missed from work due to a physical illness, or injury, or mental or emotional problem (including those missed because of hospitalizations). MEPS questions can be used to measure missed days of school if survivors are enrolled in school or training. For all participants, including those who are not employed or are on leave, we will assess lost household productivity by measuring days spent in bed, defined in MEPS as half days or more spent in bed because of physical illness or injury, or mental or emotional problems. We will also use the *Work Limitations Questionnaire-Short Form (WLQ-SF)*[39] to assess productivity. The WLQ has 25 items, and 4 subscales that assess limitations in 4 job dimensions (time, physical, mental/interpersonal/output). The subscale scores represent the percentage of time in the previous 2 weeks that participants may be limited in performing in the specific dimension. An overall WLQ Productivity Loss Score is the weighted sum of the 4 subscale scores and indicates the percentage decrement in productivity. The WLQ demonstrated high validity and reliability[39, 57] and has been used in cancer survivor populations.[58-60] While developed to assess productivity at paid work, it has been used with homemakers as well.[61]

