Adjustment for Multiple Inference

A False Discovery Rate (FDR) approach[85] will be utilized to adjust inferential results for multiple inferences on the same body of data, separately for the primary analyses and the exploratory analyses. The FDR is the expected proportion of true null differences among those that are declared “significant”. The FDR will be set at 10%. All research products will disclose the number of inferences conducted and whether outcomes were primary or exploratory. As shown above, the sample is well powered to detect relevant effect sizes on the primary outcomes, even after multiplicity adjustment.

Heterogeneity of Intervention Effects

Rationale. We have developed the intervention to be flexible and responsive to the needs of a diverse group of breast cancer survivors. However, our diverse sample will give us the opportunity to identify any unanticipated moderator effects. Therefore, we will explore whether there are subgroups of participants who benefited most and least during the study, as per the primary outcomes.

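### The only planned moderator analysis fits trees to each participant's own change with group as one ordinary predictor, so it cannot reliably separate prognosis from effect modification

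*Combined protocol and SAP*

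**What the plan says.** The Rationale paragraph under Heterogeneity of Intervention Effects (section 9) states the aim: "our diverse sample will give us the opportunity to identify any unanticipated moderator effects", and "we will explore whether there are subgroups of participants who benefited most and least during the study". Section 6, under Participation ability, adds a questionnaire item on the source of the restrictions "so that we can determine if the source of the restrictions moderates the effect of the intervention". All three statements concern differences in the effect of the intervention.

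The Recursive partitioning paragraph describes the classical approach, with interaction tests one characteristic at a time, and then replaces it with trees. On the outcome it says "The target variables for the CART modeling will be the average change from baseline in each primary outcome". On the predictors it says "Regression tree models for these target variables will be fitted using as predictors the group assignment and selected baseline characteristics", and "These baseline characteristics will include indicators of pertinent subpopulations of interest: site, race, income, age, etc". On fitting it says "We will implement the conditional inference approach[87] to fit the tree models and use repeated 10-fold cross-validation to determine the final tree size". The trees are compared across three imputed datasets, read from the characteristics of the resulting groups, and declared exploratory.

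No step targets the between-group difference, forces a split on group, tests group-by-characteristic interaction, or reports a treatment difference in each terminal node.

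**The concern.** A moderator is a characteristic across which the between-group difference varies. Under Modeling, section 9 itself defines the overall treatment effect as a between-group difference in change. The tree has a different target: it looks for whatever best predicts an individual's change, whichever arm she is in. Characteristics that predict recovery equally in both arms can take the early splits. Group is then tested only within the smaller nodes that remain, and it may pass the split test in one branch and fail in its neighbour. The tree then displays a treatment difference for some women and none for others, although the true effect is the same for all.

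At stake is how the published profiles of who benefited are read. They could largely describe who recovers anyway, and where the sample became too small for group to be selected. Because interaction tests are dropped, no second planned analysis would reveal this.

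**Working it through.** **Inputs from the documents (section 9, Sample Size Determination; randomization scheme in section 6).** 300 enrolled and 240 completing; 1:1 allocation; three post-baseline assessments; PROMIS SD 10; minimally important difference 3.94 for satisfaction; within-subject correlation rho 0.2-0.8.

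**The plan's own figures.** The heterogeneity analysis has no stated figure, so the sample-size inputs were checked. With n per arm = 2(z_(1-alpha/2) + z_0.80)^2 SD^2 (1 + 2 rho)/(3 delta^2) and alpha = 0.05/3, PROMIS gives 62.9 and 116.9, matching the stated 63 and 117. FACT-B (SD 24, difference 11.2) gives 44.9 and 83.3, against the stated 45 and 83; at alpha 0.017 the upper value is 82.95. The inputs reproduce.

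**SD of the tree's target.** Var(average of T2-T4 minus T1) = SD^2 (4/3)(1 - rho). At rho 0.5 this is 66.7, so the SD is 8.16 (10.33 at rho 0.2, 5.16 at rho 0.8). Its correlation with the baseline score is -0.5/sqrt(0.667) = -0.61, so the baseline score strongly predicts change through regression to the mean.

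**Why the tree misleads.** Take seven predictors and a 5% split test with Bonferroni adjustment: the critical z is 2.69. For a balanced binary predictor in a node of size n, the standard error is 2 x 8.16/sqrt(n).
- n = 300: SE 0.942. Group has expected z = 3.94/0.942 = 4.18. A 4-point prognostic factor has 4/0.942 = 4.25, so it takes the first split about as readily as group.
- n = 150: SE 1.333. Group has expected z 2.96 and passes with probability about 0.61.
- n = 75: SE 1.884. Group has expected z 2.09 and passes with probability about 0.27.

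If a prognostic factor splits first, a uniform effect passes in exactly one of the two halves with probability 2 x 0.605 x 0.395 = 0.48. This ignores later splits and competition between predictors, which the simulation includes.

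**Simulation.** Conditional inference trees on average change; predictors group, site, race, income, age, chemotherapy and time since treatment; minimum node 20, minimum leaf 7; N = 300; rho 0.5. Assumed, not in the documents: two prognostic factors (age above or below 57, and chemotherapy), each shifting change by 0, 2.5 or 4 points in both arms. Differential benefit means that the tree uses group and the implied treatment difference is not the same for everyone. Unpruned trees had 1,000 runs; trees sized by repeated 10-fold cross-validation had 250. A second, independent unpruned check is in brackets.

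| Truth | Tree shows differential benefit: unpruned | Cross-validated |
|---|---|---|
| Uniform 3.94, no prognostic factor | 8% (7%) | 3% |
| Uniform 3.94, factors of 2.5 | 47% (51%) | 25% |
| Uniform 3.94, factors of 4 | 76% (78%) | 56% |
| Uniform 3.94, baseline score as splitter, no other prognostic factor | 91% | 78% |
| Effect differs by 3.94 between sites, factors of 4 | 80% | 58% |

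Further results, unpruned / cross-validated:
- Uniform effect, factors of 4: the implied spread in treatment difference was at least 3.94 points in 65% / 45%, and group never appeared in 19% / 26%.
- No treatment effect, factors of 4: 95% / 94% of trees split on baseline characteristics only.
- Strong site moderator (0 versus 7.88): found in 99% / 99% without prognostic factors and about 90% / 83% with factors of 4.
- N = 240, unpruned, uniform effect: 32% at 2.5 points and 64% at 4.

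**Comparator.** Trees that split only on the treatment-effect score, after adjustment for main effects, gave false differential benefit in about 3-7% and found the strong site moderator in about 91-95%.

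**The case against.** The strongest defence has four parts.

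First, the analysis is declared exploratory, and section 9 requires exploratory status to be disclosed. That stands, and it limits the weight of any finding. But the label warns about chance findings, and the problem here is the target of the split.

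Second, cross-validation is planned and does help: 47% falls to 25%, and 76% to 56%. It limits overfitting of change but does not make the tree look for differences in effect. The same holds for comparing three imputed datasets.

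Third, group is a candidate predictor, so moderators can surface. A reader might infer that the tree finds prognosis instead of moderators. The results do not support that: strong moderators are usually found. Nor does the error fall evenly on all characteristics. Site, not prognostic in these simulations, was falsely implicated in about 1% of cross-validated trees (uniform effect, factors of 4), against 23% when site truly moderated by 3.94. False moderation arises mainly through characteristics that predict recovery.

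Fourth, the size depends on assumptions. A reader might take rates near 80-90% as typical. The 91% / 78% needs the baseline score as a splitter, and the plan's open-ended list neither names nor excludes it. With no prognostic candidate the rate is 3-8%.

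It is also tempting to say that women in a branch without a group split will be declared not to benefit, or that BA/PS will be withheld from them. The documents say neither.

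**Conclusion.** The concern holds in a limited form. The plan asks which characteristics modify the treatment effect, and its only analysis for that question fits individual change. Under a uniform effect of 3.94 points, with N = 300 and rho 0.5, false differential benefit appears in about 3-8%, 25-51% or 56-78% of trees when two factors shift change by 0, 2.5 or 4 points, and more often if the baseline score is a splitter. At factors of 4, the overall display of differential benefit barely distinguishes a moderate real moderator (80% / 58%) from none (76% / 56%).

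The prognostic strengths are assumed, and the rates are given for rho 0.5 only, while the plan allows 0.2-0.8. The primary inference and the sample size are unaffected. A reader should not infer that the trial's main conclusions are at risk.

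**What to change.** Keep recursive partitioning and the candidate characteristics, but split on the treatment effect. Use either model-based partitioning with group coded -0.5/+0.5, or a group-by-characteristic interaction test with main effects of the candidates and the baseline score in the model. Use multiplicity-adjusted stopping in either case.

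The coding matters. A node model with 0/1 group coding and only the baseline score lets omitted prognostic factors leak into the group coefficient. In a check under a uniform effect it gave false first splits in 38% (factors of 2.5) and 82% (factors of 4), against about 5% with a centred group term or an interaction test with main effects. A separate check of 0/1 coding ranged from 11% to 59% and from 23% to 97%, depending on how the scores were handled.

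Report the between-group difference with its interval in every terminal node, keep the exploratory label, and state that a branch without a group split is not evidence of no benefit.

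The cost is SAP wording and a little more analysis work in R, which is already named. Section 10 says that only data collection remains and that inferential analyses follow its completion, so the change can be made before analysis. The downside is that many trees will have no split. That is correct when the effect is uniform, but power for moderate moderators is also low: with a 3.94-point difference between sites and factors of 4, the effect-targeted tree picked site in only 26% of 250 runs.
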